## 9.4. Safety evaluations

The study will include the following evaluations of safety and tolerability:

### Adverse Events

Adverse events will be reported by the subject (or, when appropriate, by a caregiver, surrogate, or the subject's legally acceptable representative) for the duration of the study.

### Clinical Laboratory Tests

All laboratory tests should be performed at the laboratory of the investigational site: laboratory certificates or accreditation and normal ranges must be submitted before the patient's enrollment.

### **Electrocardiogram**

Vital Signs (pulse, temperature, blood pressure, respiration rate)

### **Physical Examination**

Any clinically significant abnormalities persisting at the end of the study will be followed by the investigator until resolution or until reaching a clinically stable endpoint.

**Safety and feasibility of treatment:** severe hematological toxicities (grade 3-4) expected.

Grading of toxicity will be defined according to the International Common Toxicity Criteria, version 3.0 (12/12/2003)

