### **1.1.2. Liposomal cytarabine (Depocyte) background**

Potential risks of depocyte.

The following adverse event occurring in two or more patients receiving DepoCyte in the phase III/IV clinical studies were associated with patient outcomes categorized as serious. The events are listed by descending order of frequency within body system.

Body as a Whole: headache, fever, asthenia, back pain, hydrocephalus, pain, sepsis, neoplasm, injection site reaction, infection, mucous membrane disorder, abdominal pain, chills, accidental injury

Nervous system: seizure, psychosis (hallucinations/delusions), confusion, arachnoiditis, intracranial hypertension, somnolence, meningitis, agitation, neuropathy, hypoesthesia, liquor alterations, dizziness, gait disorders, coma, subdural haematoma, meningism, facial paralysis.

Digestive system: nausea, vomiting, gastrointestinal haemorrhage, intestinal occlusion, diarrhoea, anorexia

Cardiovascular system: cardiac arrest, pulmonary embolus, hypotension, syncope, deep thrombophlebitis.

Hemic and Lymphatic system: neutropenia, thrombopenia, anaemia.

Metabolic and Nutritional Disorder: dehydration, hyperglycaemia, hyponatremia, alkalosis

Respiratory system: pneumonia, apnoea, dyspnoea, bronchitis

Special senses: deafness

Urogenital system: urinary tract infection

Skin and Appendages: sweating

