## **2. OBJECTIVES**

### **2.1. Primary objective**

To demonstrate safety and feasibility of the R-CHOP regimen in combination with intrathecal liposomal cytarabine and systemic intermediate-dose methotrexate followed by loco-regional radiotherapy in untreated patient with stage I and II Primary Testicular Lymphoma

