#### **3.1. Statistical plan and rationale**

The previous IELSG 5 retrospective analysis on 373 patients with testis lymphoma, showed a PFS of 48% at 5 years in the entire population, regardless of the type of treatment.

The IELSG 10 prospective clinical study was designed with a sample size of 50 patients defined to reject the null hypothesis of a PFS of 50% under the alternative hypothesis that the true PFS is 70% with a 5% significance level (two-sided) and 80% power.

The early results of IELSG 10 study seem to suggest that Rituximab-CHOP regimen plus intrathecal prophylaxis with methotrexate may reduce the incidence of CNS relapses and, therefore, improve the outcome. However, the follow up is not yet adequate to allow any sound conclusion and, at present, it is unclear on which estimation of PFS should a sample size be calculated. According to the recruitment rate of the previous IELSG 10, assuming a similar number of participating centers, we may expect to enroll approximately 35 cases in 3 years. At that point, the feasibility of the design should be adequately evaluated and the follow up data from the previous IELSG 10 study should be mature enough for a careful calculation of the sample size in order to transform this pilot study in a formal phase II trial.

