## 11.2. Procedures

### 11.2.1. All Adverse Events

All adverse events other than disease progression will be reported from the time a signed and dated informed consent form is obtained until 30 days after the 1st dose of study drug. All events that meet the definition of a serious adverse event will be reported as serious adverse events, regardless of whether they are protocol-specific assessments.

All adverse events, regardless of seriousness, severity, or presumed relationship to study therapy, must be recorded using medical terminology in the source document and the CRF. Whenever possible, diagnoses should be given when signs and symptoms are due to a common etiology (e.g. cough, runny nose, sneezing, sore throat, and head congestion should be reported as "upper respiratory infection"). Investigators must record in the CRF their opinion concerning the relationship of the adverse event to study therapy. All measures required for adverse event management must be recorded in the source document and reported according to sponsor instructions.

All grade 3 and 4 adverse events, considered related, must be followed until resolution of the event, or the event improves to a grade 2 or better. The events of interest in the table above of grade 2 or higher will be followed until grade 1 or better. The unresolved aforementioned events will be followed for a maximum of 6 months.

Sections of the CRFs containing adverse event information will be submitted by the investigator to a representative of the sponsor. Serious adverse event reports will be submitted as described in Section 11.2.2, Serious Adverse Events.

The investigator-Sponsor must report adverse events to the appropriate Independent Ethics Committee/Institutional Review Board (IEC/IRB) that approved the protocol unless otherwise required and documented by the IEC/IRB. The Investigator-Sponsor assumes responsibility for appropriate reporting of adverse events to regulatory authorities. The Investigator-Sponsor shall also report all serious adverse events to the pharmaceutical companies providing the study medication.

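### The primary objective, safety and feasibility, has no endpoint, denominator or criterion, and the one line labelled for it names only haematological toxicity

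*Combined protocol and SAP*

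**What the plan says.** Section 2.1 gives the primary objective: "To demonstrate safety and feasibility of the R-CHOP regimen in combination with intrathecal liposomal cytarabine and systemic intermediate-dose methotrexate", followed by radiotherapy. Section 3.1 sets the size at about 35 patients from expected accrual and says that at that point "the feasibility of the design should be adequately evaluated", as one step towards a formal phase II trial. It gives no criterion.

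Section 9.3 defines response, overall, event-free, progression-free, disease-free and lymphoma-specific survival. It defines neither safety nor feasibility. The only line that carries that label closes Section 9.4 and reads "severe hematological toxicities (grade 3-4) expected". The next sentence is general: "Grading of toxicity will be defined according to the International Common Toxicity Criteria, version 3.0".

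Data collection is wider than that line. Section 11.2.1 states: "All adverse events, regardless of seriousness, severity, or presumed relationship to study therapy, must be recorded". Section 1.1.2 lists serious nervous-system events for the intrathecal drug, among them "seizure, psychosis (hallucinations/delusions), confusion, arachnoiditis, intracranial hypertension".

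**The concern.** The secondary endpoints have definitions and the primary objective has none. Someone who analysed the trial from the labelled line alone would tabulate grade 3-4 haematological toxicity. That table would not show how many patients received the four intrathecal doses, the two methotrexate courses and radiotherapy, nor how often neurological toxicity occurred. These are the parts that the trial adds to immunochemotherapy.

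Because no measure, analysis set or minimum is fixed, each can be chosen once the data are known. The report could then say demonstrated or not demonstrated on the same results, and one input to the decision on a formal phase II trial would be open to choice after the fact.

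**Working it through.** **1. Is there a figure to reproduce?** The 35 patients come from expected accrual. No rate, alpha, power or precision is attached to them, so there is nothing to recompute. The only powered figure in the document is the 50 patients of the earlier IELSG 10 study (PFS 50% vs 70%, two-sided 5%, power 80%). It reproduces with the null variance: n = (1.960 + 0.842)² × 0.50 × 0.50 / 0.20² = 49.06, rounded up to 50. It concerns PFS in another study and gives no basis for safety or feasibility here.

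**2. Does another section supply the missing measure?**
- Section 10.1 defines study completion by assessments at week 30 and also counts patients who stop for lack of efficacy as completers. That does not measure treatment delivery.
- Section 9.3.1 counts stopping for toxicity in event-free survival, but this is a secondary endpoint and pools it with progression and death.
- Section 10.2 stops treatment for grade 3 or higher toxicity lasting over two weeks. That is a rule for the individual patient and sets no trial-level criterion.

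**3. Why the denominator matters.** Sections 6.2.1 and 9.1.4 remove patients without CR or PR after cycle 3. The intrathecal doses fall in cycles 2 to 5, so a removed patient can have had at most two of four, and no methotrexate. Suppose, as an assumption, that 5 of 35 are removed at that point and 28 of the other 30 receive everything. Delivery is then 28/35 = 80% of those registered, or 28/30 = 93% of those allowed to continue. The plan does not say which would be reported.

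**4. What 35 patients can show.** Clopper-Pearson limits for x of n are the α/2 quantile of Beta(x, n−x+1) and the 1−α/2 quantile of Beta(x+1, n−x). Counts are illustrative.

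| x/35 | Estimate | Exact 95% CI |
|---|---|---|
| 0 | 0% | 0 to 10.0% |
| 2 | 5.7% | 0.7 to 19.2% |
| 5 | 14.3% | 4.8 to 30.3% |
| 28 | 80.0% | 63.1 to 91.6% |
| 30 | 85.7% | 69.7 to 95.2% |

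The chance of seeing at least one event is 1 − (1 − p)³⁵: 29.7%, 50.7%, 83.4% and 97.5% for true rates of 1%, 2%, 5% and 10%. Description is therefore possible. Precision for methotrexate would be lower, because fewer patients reach it.

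**5. Could a criterion work at this size?** Two rules from the exact binomial tail P(X ≥ r | 35, p). The document gives none of these rates.

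| Unacceptable / target | Success if | One-sided alpha | Power |
|---|---|---|---|
| 65% / 85% | ≥ 28 | 4.2% | 85.6% |
| 70% / 90% | ≥ 30 | 2.7% | 86.8% |

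These are one-sided 5% rules, so a two-sided 95% interval does not match them: 28/35 passes the first rule although its lower limit, 63.1%, is below 65%, and 30/35 passes the second with a lower limit of 69.7%, below 70%. The one-sided 95% lower limits (the lower ends of two-sided 90% intervals) are 65.7% and 72.3%, and agree with the rules.

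**6. Are the safety data secure?** Section 9.1.1 monitors adverse events to 30 days after the end of treatment, and Section 9.4 has them reported for the duration of the study. Section 11.2.1 reports them "until 30 days after the 1st dose of study drug". In Attachment 9 the intrathecal doses fall on days 21, 42, 63 and 84, and methotrexate on days 126 and 140.
- Counted from day 0, the Section 11.2.1 window closes on day 30: one of four intrathecal doses falls inside it and neither methotrexate course does.
- Counted from the first liposomal cytarabine dose (Section 12.5 identifies that product as the study drug), it closes on day 21 + 30 = 51: two of four intrathecal doses and no methotrexate course.

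Serious events are reported separately under Section 11.2.2, so the gap mainly concerns non-serious events.

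**The case against.** The strongest reply is that the labelled line states an expectation. Naming one expected toxicity does not exclude others. Section 9.4 also lists adverse events, laboratory tests, ECG, vital signs and physical examination as safety evaluations. Events are graded and attributed (Section 11.1.2), and deaths are reported as serious events. Cerebrospinal fluid is examined at the intrathecal doses, and methotrexate levels are measured. This stands. A reader might infer that the primary question cannot be answered at all for the added components, or that fatal and neurological events are left out. The document does not support either inference.

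A reader might also infer that haematological toxicity reflects mainly the R-CHOP backbone. Section 1.1.2 lists neutropenia, thrombopenia and anaemia for the intrathecal drug too, and the plan gives no R-CHOP benchmark by which to apportion them.

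Finally, this is a non-comparative pilot in a rare disease, and the step to a formal phase II trial also waits on mature IELSG 10 follow-up. A descriptive aim without a powered test is defensible, so the feasibility result is not the sole basis for that decision. But the objective is worded as "To demonstrate safety and feasibility of the R-CHOP regimen", and even a descriptive aim needs a stated measure and denominator. The reply supplies neither.

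**Conclusion.** The concern holds in a limited form. The primary objective has no matching endpoint, analysis set or criterion, and the line labelled for it covers neither treatment delivery nor neurological toxicity. Toxicity of the added components can be described from the recorded events, provided that the windows are reconciled. What the plan cannot support is a pre-specified conclusion that safety and feasibility were demonstrated.

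As a measure of the room left open, 28 of 35 is compatible with true delivery from 63.1% to 91.6%, and the choice of denominator alone moves the estimate from 80% to 93% under the assumed five removals. The counts and the 65/85% and 70/90% pairs are illustrations; they show that a criterion is workable with 35 patients and do not say what it should be. The change should be made, since the objective otherwise has no pre-specified answer.

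**What to change.** Replace the labelled line in Section 9.4 with two measures.

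1. **Feasibility.** The proportion of all registered patients who received every planned component (six R-CHOP cycles, four intrathecal doses, two methotrexate courses, radiotherapy), with an exact 95% CI. Show delivery per component among patients who reached it as well. Split reasons for non-delivery into removal for SD or PD, toxicity, refusal and other, so that protocol-mandated removal after cycle 3 is not read as poor deliverability. Judge the result against a sponsor-set minimum fixed in advance, at an interval level that matches the decision rule.
2. **Safety.** The proportion with any grade 3-5 non-haematological toxicity, with neurological events and treatment-related deaths shown separately and by treatment phase. Keep haematological toxicity as a supporting table.

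Reconcile the adverse event windows in Sections 9.1.1, 9.4 and 11.2.1 so that events during the later intrathecal doses and both methotrexate courses are captured.

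The cost is mainly wording. Adverse events and reasons for withdrawal already go on the CRF (Sections 11.2.1 and 10.3). The CRF itself is not among the documents, so fields for per-component delivery need checking. The real price is that the sponsor commits in advance to a minimum that the trial may miss.

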## **10. SUBJECT COMPLETION / WITHDRAWAL**

### **10.1. Completion**

A subject will be considered as having completed the study if he/she has completed all assessments at week 30 of the [open label] treatment phase.] [Subjects who discontinue study treatment due to lack of efficacy are also considered to have completed the study.]

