##### IT CHEMOTHERAPY

Depocyte® 50 mg on day 0 of cycles 2, 3, 4 and 5 of R-CHOP

R-CHOP courses will be repeated every 3 weeks. The prophylactic intrathecal Depocyte will be given for a total of 4 times, during R-CHOP cycles.

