##### Consolidation phase

Begins three weeks after the R-CHOP/IT therapy completion.

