##### INTERMEDIATE-DOSE MTX

Methotrexate 1.5 g/m^2

It will be administrated diluted in 500 ml of normal saline solution (NaCl 0.9%). A urine flow  $\geq$  125 ml/hr has to be recorded in the 12 hrs before the MTX administration.

For MTX handling and administration see Attachment 5.

Intermediate-dose Methotrexate courses will be repeated every 14 days for 2 cycles.

All patients will undergo interim restaging procedures after the 3rd course (and before the 4th) of R-CHOP. Clinical response will be re-assessed at the end of planned treatment, one-two month after the completion of the whole therapy, including radiotherapy. Additional imaging studies during the treatment phase will be done only if clinically indicated.

Patients with progressive disease at any time will be withdrawn from the study.

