### 6.2.1. CHOP dose modification

Patients will start R-CHOP every 21 days if neutrophils  $> 1.0 \times 10^9/L$  and platelets  $> 75 \times 10^9/L$ .

- If neutrophils are  $< 1.5 \times 10^9/L$  and/or platelets  $< 75 \times 10^9/L$ : R-CHOP must be delayed (after 7 days, on day +28)
- If Neutrophils  $\geq 1.5 \times 10^9/L$  and Platelets  $\geq 75 \times 10^9/L$  on Day +28 R-CHOP will be performed with no change in dose

In case of neutropenia Filgrastim or Peg-Filgastrim should be added in the following course of chemotherapy according to "2006 update of recommendations for the use of white blood cell growth factors: an evidence-based clinical practice guideline" (Journal Clinical Oncology 2006 24:3187-3205), and to primary physician judgment in order to avoid delay. Primary prophylaxis of neutropenia with filgastrim or peg-Figastim is allowed in patients over 65 years of age according to the same guidelines.

- Dose modification for sensory neuropathy. No modification as long as neuropathy does not affect function. Any decrease of function (grade 3/4) would lead to dose reduction of vincristine by 50%. If grade 4 toxicity persists after reduction of vincristine by 50%, vincristine may be eliminated from subsequent cycles.
- Prednisone dose may be decreased by 50% or discontinued if patients have increase in serum glucose to  $> 300 \text{ mg/dl}$ , or other psychological disturbances such as psychosis or anxiety attacks.

Just patients who have achieved PR/CR after three cycles of CHOP will continue therapy. All other patients will be removed from the study and will be considered for other possible therapies according to the local policy.

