# 9. STUDY EVALUATIONS

## 9.1. Study Procedures

### 9.1.1. Overview

Patients participation will include:

1. The pretreatment (screening) phase will be 30 days for all laboratory tests and radiographic imaging phase and up to 60 days for orchectomy and bone marrow evaluation.
2. The open label treatment phase will extend from the first day of the first course of R-CHOP to a maximum of 6 courses.
3. The consolidation phase will extend from the first day of the first course of Intermediate-dose MTX to the end of radiotherapy.
4. The follow-up phase will begin after the completion of the consolidation phase. Follow-up will continue until disease progression (PD), patient withdrawal, death or the study completion (expected to be 36 months from the date of the last patient's end of therapy).

Hematology results must be available and reviewed by the investigator to evaluate for possible hematological toxicity.

All subjects will be monitored for adverse events throughout the study and for 30 days after the end of treatment.

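### Section 10.1 ties study completion to week 30 of a treatment phase that ends at about week 18, and counts as completers patients whom other sections withdraw

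*Combined protocol and SAP*

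**What the plan says.** Section 10.1 has two routes to completion. By the first, a subject must have "completed all assessments at week 30 of the [open label] treatment phase". By the second, which stands in square brackets, "Subjects who discontinue study treatment due to lack of efficacy are also considered to have completed the study".

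Section 9.1.1 defines the phase that the first route relies on: "The open label treatment phase will extend from the first day of the first course of R-CHOP to a maximum of 6 courses". It makes consolidation a separate, later phase: "The consolidation phase will extend from the first day of the first course of Intermediate-dose MTX to the end of radiotherapy". Section 6.1.1 gives the spacing: "R-CHOP courses will be repeated every 3 weeks". It says of consolidation: "Begins three weeks after the R-CHOP/IT therapy completion".

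Three other places bear on the second route:
- Section 9.1.4 takes patients with stable or progressive disease after the third course off the study and evaluates them as treatment failures.
- Section 10.2 lists progression and non-response after course three among the reasons to stop treatment.
- Section 10.3 lists discontinuation of study treatment as a reason for withdrawal from the study.

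Section 9.1.1 also uses study completion in another sense, for a date expected 36 months after the last patient's end of therapy.

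**The concern.** The first route names a time point that the phase does not contain. The second gives a patient a status that two other sections contradict: the same man can be a completer under 10.1, withdrawn under 10.3 and a treatment failure under 9.1.4.

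Safety and feasibility form the primary objective (section 2.1). Section 3.1 expects feasibility to be evaluated once about 35 patients are enrolled, before the pilot becomes a formal phase II trial. Section 10.1 is the only place that says when a subject counts as having completed, so it is the rule an analyst would be likely to use when tabulating disposition or describing how many patients got through the programme. It also affects data collection, because section 10.3 asks for a documented reason when a subject withdraws before completing. A non-responder already classed as a completer could fall outside that requirement.

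**Working it through.** **1. End of the open-label treatment phase.** Inputs: at most six courses (9.1.1), 21 days apart (6.1.1).
- Course starts: days 0, 21, 42, 63, 84, 105. These match Attachment 9.
- End of phase: 6 × 21 = day 126; 126 / 7 = week 18.0. This agrees with methotrexate starting on day 126 in Attachment 9 and in week 18 in the synopsis.
- Week 30 is day 210. Gap: (210 − 126) / 7 = 12 weeks.

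**2. Allowing for delay.** Section 6.2.1 has a 7-day delay step. Applied to each of courses 2 to 6: 126 + 5 × 7 = day 161 = week 23.0, still 7 weeks short. To stretch the phase to week 30, those five courses would have to slip by 84 / 5 = 16.8 days each.

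**3. Is anything scheduled at week 30?** No visit in section 9.1 or Attachment 9 carries that label. The nearest candidate is the end-of-treatment restaging in 9.1.6, set 1–2 months after all therapy and therefore outside the treatment phase.

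**4. Looser reading: week 30 counted from first dose.** Inputs: "Intermediate-dose Methotrexate courses will be repeated every 14 days for 2 cycles", so courses on days 126 and 140; radiotherapy of 10–20 fractions (section 7). I assume five fractions per week, which the protocol does not state, giving 2–4 weeks. One to two months is taken as 30.4–60.9 days. The documents give several radiotherapy start times. Restaging window = (radiotherapy end + 30.4 to 60.9 days) / 7.

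| Radiotherapy start | Start (week) | Restaging, 2 weeks of RT | Restaging, 4 weeks of RT |
|---|---|---|---|
| 3.2: two weeks after methotrexate (day 154) | 22.0 | 28.3–32.7 | 30.3–34.7 |
| Section 7: three weeks after chemotherapy (day 161) | 23.0 | 29.3–33.7 | 31.3–35.7 |
| Attachment 9: day 165 | 23.6 | 29.9–34.3 | 31.9–36.3 |
| Synopsis: week 24 (day 168) | 24.0 | 30.3–34.7 | 32.3–36.7 |

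Week 30 lies inside the window on three of these eight paths and before it opens on five. The synopsis and section 3.2 also allow radiotherapy alongside R-CHOP in bilateral disease. Taking treatment then to end with methotrexate on day 140, restaging runs from (140 + 30.4) / 7 = week 24.3 to (140 + 60.9) / 7 = week 28.7, so week 30 comes after it.

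**5. Second route.** A patient with stable disease after course three stops treatment for want of effect. Section 10.1 makes him a completer; 9.1.4 and 10.3 do not. With the first route empty, he and patients like him are the only ones the literal rule counts.

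The design figure in section 3.2 was not available in the text and was not used.

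**The case against.** The best defence is that 10.1 is a disposition rule for the study. It is not a measure of treatment delivery, and little depends on it. Much of this stands. The only text under safety and feasibility in section 9.4 concerns grade 3–4 haematological toxicity, and no section defines feasibility as a completion rate. The defined outcomes are protected: 9.1.4 evaluates non-responders as failures, 9.3.1 makes stopping treatment for any reason an event for event-free survival, and 9.3 counts unassessed patients as non-responders. The square brackets also look like template options left unresolved, so the second sentence may not have been meant to operate.

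Three stronger readings are tempting, and the documents do not support them:
- A reader might infer that nobody can complete. The second sentence of 10.1 contradicts this; only the week-30 route is empty.
- A reader might infer that the feasibility result is inflated, at 1/35 = 2.9 percentage points per patient stopped for lack of efficacy. That presumes an endpoint the protocol does not contain, and no expected number of such stops is given.
- A reader might infer that week 30 always precedes restaging. That depends on a single radiotherapy path; across the stated paths, week 30 can fall before, within or after the window.

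The defence does not supply a meaning for the week-30 time point or reconcile 10.1 with 9.1.4 and 10.3.

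**Conclusion.** Wrong as written. The treatment phase ends at week 18 on schedule and at week 23 with a 7-day delay at every later course, so the week-30 criterion lies 12 or 7 weeks beyond it and matches no labelled visit. This result uses only the protocol's own course count, interval and delay step. Reading week 30 as time since first dose does not rescue the rule: restaging falls at about weeks 28–37 with sequential radiotherapy and about weeks 24–29 with concomitant radiotherapy. Those ranges, unlike the week-18 result, rest on the assumed conversion of months to days; the sequential range also rests on five fractions per week.

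The second route conflicts directly with 9.1.4 and 10.3, and taken literally it leaves only patients in whom treatment failed as completers. The consequence is limited to the completer count. Event-free survival and response stand, and no stated feasibility formula is broken. If 10.1 were used to report feasibility, the count would be wrong.

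**What to change.** Reconcile sections 9.1.1, 9.1.4, 9.1.6, 10.1 and 10.3 and Attachment 9. In 10.1:
- Replace the week-30 rule with programme completion, defined as delivery of the planned components plus the end-of-treatment restaging in 9.1.6.
- Define completion of follow-up separately and report the two side by side.
- Remove the brackets, and do not count discontinuation for lack of efficacy as programme completion, in line with 9.1.4 and 10.3.

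This is a counting rule and changes no treatment or stopping rule. The radiotherapy start times differ between the synopsis, section 3.2, section 7 and Attachment 9; the sponsor should reconcile them so that the restaging window has one reference date. The cost is one reworded section and possibly a slightly lower reported completion rate.
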